4.6.4.3 Tipping Point Analysis

To assess robustness of the primary efficacy analysis result, a tipping point analysis will be conducted. In this analysis, multiple imputation (see Section 4.9.1.2 for details) will be employed to impute the missing mRS scores at Day 90.

In these imputations, the log-odds for a favorable outcome ($mRS \leq k$) will be penalized in the TNK treatment group via an additional term Δ (see Tang 2018). Thus, $\exp(-\Delta)$ is the additional term in the odds ratio of a favorable outcome between the TNK and Placebo groups under various assumptions of missing data mechanism, where $\Delta=0$ corresponds to missing at random (MAR) and $\Delta>0$ denotes missing not at random (MNAR). The value of Δ will be gradually increased until the p-value crosses the pre-specified nominal alpha level (0.003 at interim, 0.049 at final analysis).

Rubin's standard error will be used in the normal approximation formula to construct confidence intervals and p-values (Little et al. 2002). If the p-value does not reach the nominal alpha level within a reasonable range of data, then it will be concluded that the finding about the treatment difference is sufficiently robust to violations of the MAR assumption. If the p-value exceeds the nominal alpha level for some value of Δ , then a plot of p-values versus Δ will be provided. A monotone smoother will be added to the plot to help locate the tipping point.

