4.9.1.2 Multiple Imputation

Missing mRS data will be imputed using a sequential regression method. Particularly, mRS will be sampled from a multinomial distribution. This distribution will be estimated by ordinal logistic regressions, using baseline covariates and the previous mRS value.

The ordinal logistic regressions estimate the cumulative odds for achieving an mRS outcome of at most k :

$$\text{logit}[\Pr(mRS_t \leq k)] = \alpha_{kt} + X\beta_t + mRS_{t-1}\delta_t$$

where t is the time point index (Day 5, Day 30, Day 90), $k = 0$ to 5 , α_{kt} are intercepts, X is the design matrix for the baseline covariates and β_t are the corresponding regression coefficient vectors, and mRS_{t-1} is the previous mRS result (baseline, Day 5 or hospital discharge, or Day 30) with its coefficient δ_t . The list of covariates will include age, sex, race (white vs. non-white), baseline NIHSS, occlusion type and discharge destination (home vs. non-home).

Separate regressions will be fitted for each treatment group to avoid any assumptions about the treatment effect. In order to limit the number of parameters and prevent estimation issues, it will be assumed that the covariate effects β_t and δ_t do not depend on k (the proportional odds assumption). The model may be revised if estimation issues are encountered (e.g. quasi-complete separation). Logit is the usual link transformation, associated with a logistic regression.

For each fixed value of Δ , imputation is carried out in the following steps. These steps are repeated to impute missing mRS first at Day 30, then at Day 90 (using imputed Day 30 results):

- Fit the ordinal logistic regressions for mRS at time t , separately in the TNK and placebo groups.
- For patients with missing mRS at time point t , obtain the predicted cumulative probabilities. In the placebo group, use the probabilities predicted by the model. In the TNK group, recalculate the probabilities using the following equation.

$$\text{logit}[\Pr(mRS_t \leq k)] = \widehat{\alpha}_{kt} + X\widehat{\beta}_t + mRS_{t-1}\widehat{\delta}_t - \Delta$$

where $\widehat{\alpha}_{kt}$, $\widehat{\beta}_t$ and $\widehat{\delta}_t$ are the estimated coefficients from the TNK model. The penalty term Δ reduces the odds for a favorable outcome. This penalty will only be applied the first time mRS is missing for the patient; its effect will be propagated to subsequent time points by the mRS_{t-1} term in the regression.

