hr=hour; MT=mechanical thrombectomy; PBO=placebo; R=randomized; TNK=tenecteplase.

Note: The primary endpoint will be assessed at the Day 90 visit.

Appendix 3

SAS Code for Statistical Analysis

Analysis	Sample Code
Ordinal mRS parametric analysis and the test for proportional odds	<pre>proc logistic; class trt x1-x4; model Y = trt x1-x4; run;</pre> 
where Y is the ordinal mRS score, trt is treatment, and x1-x4 are randomization stratification factors. The score test for proportional odds is generated by default.

Multiple imputations for the tipping point analysis, ordinal mRS	
I. Obtain prediction probabilities for mRS at time point t.
 <pre>proc logistic; by trt; ... model Yt = ... Yp; output out=fit predicted=p; run;</pre> 
where Yt is the ordinal mRS score at time t, trt is treatment group, Yp is the value of mRS at the previous visit.
 
II. Apply the penalty to the predicted probabilities.
 <pre>data fit; set fit; if not missing(p) then do; oddsr=p/(1-p); newoddsr=oddsr/delta; newp=newoddsr/(1+newoddsr); end; run;</pre> 
III. Replace missing values of mRS at time t with random draws from the multinomial distribution defined by the vector of cumulative probabilities p or newp. newp is used for the values in the TNK group to impute for the first missing time point; other imputations will use p.
 <pre>data outmi; ...</pre>

	<pre> x=rand('TABLE',p0,p1-p0,p2-p1,p3- p2,p4-p3,p5-p4)-1; ... run; </pre> 
The code will be executed first to impute Day 5 mRS, then Day 30 mRS, and then again to impute Day 90 mRS. Each time only the records with non-missing covariates and previous mRS value will be supplied.

Rubin's rules for the tipping point analysis, ordinal mRS (assuming proportional odds)	<pre> proc logistic data=outmi; model Y = trt x1-x4; by _Imputation_; ods output ParameterEstimates=PE; run; proc mianalyze parms=PE; modeleffects trt; run; </pre> 
where Y is the ordinal mRS score, trt is treatment, x1-x4 are randomization stratification factors, outmi is the dataset with multiple imputations, and _imputation_ is the index of the imputed dataset.

Wilcoxon-Mann-Whitney Generalized odds ratio	Derived through programming the formulas shown in Appendix 4 in data steps.

Appendix 4

Wilcoxon-Mann-Whitney Generalized odds Ratio

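### The tipping-point analysis leaves its penalty scale undefined in the sample code, can leave some tenecteplase patients unpenalised, and gives conflicting visit sequences and patient sets (minor; sensitivity analysis only)

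*SAP*

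**What the plan says.** SAP 4.6.4.3 puts the penalty on the log-odds scale. It states that exp(−Δ) "is the additional term in the odds ratio of a favorable outcome between the TNK and Placebo groups", that Δ = 0 is the missing-at-random case, and that Δ "will be gradually increased until the p-value crosses the pre-specified nominal alpha level", which is 0.003 at the interim and 0.049 at the final analysis. SAP 4.9.1.2 gives the matching equation, in which Δ is subtracted from the fitted logit in the tenecteplase arm, and says that the penalty term "reduces the odds for a favorable outcome".

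The sample code in SAP Appendix 3 applies the penalty as "newoddsr=oddsr/delta". It does not define delta.

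On timing, 4.9.1.2 says: "This penalty will only be applied the first time mRS is missing for the patient". Its effect is then meant to reach later visits through the previous-mRS term. Appendix 3 likewise uses the penalised probability only at the first missing time point.

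On visits, the model index in 4.9.1.2 runs over Day 5, Day 30 and Day 90, and baseline is listed as a possible previous value. The step list in the same section says: "These steps are repeated to impute missing mRS first at Day 30, then at Day 90". Appendix 3 runs Day 5 first, and passes to each step only records that have a previous mRS value.

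On patients, 4.9.1 does not impute those without any post-baseline mRS and drops them from every mRS analysis. The closing note of 4.9.1.2 says that every ITT patient with baseline covariates ends with an observed or imputed Day 90 score.

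**The concern.** Protocol 6.4 names the tipping-point approach as the check on the primary result against departures from missing at random. It is the only such check in the SAP, because the primary analysis carries the last observation forward. What it delivers is a value of Δ (or a plot of p against Δ) and a judgement over a reasonable range for which no numbers are given. That output is interpretable only if the scale of Δ, the patients who receive the penalty and the patients who are imputed are all fixed in advance. Three things are unsettled:

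- The scale in the code differs from the scale in the text unless a definition is supplied.
- The once-only penalty can be used up at a visit that has no influence on Day 90.
- The visit sequence and patient set can each be read two ways.

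At stake is a reported tipping value that is mislabelled, or that looks more reassuring than it should.

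**Working it through.** **1. Scale.** The input is the tenecteplase column of SAP Table 1, where P(mRS 0–2) = 0.17 + 0.20 + 0.16 = 0.53 and the odds are 0.53/0.47 = 1.128.

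- Text: new odds = odds × exp(−Δ).
- Code: new odds = odds / delta.
- New probability = new odds / (1 + new odds).

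The text's own anchor is reproduced: at Δ = 0 the multiplier is 1 and the probability stays at 0.530. At Δ = 0.5 the text gives 1.128 × 0.6065 = 0.684, so P = 0.406.

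| Δ | Text | Code, delta = Δ | Code, delta = exp(Δ) |
|---|---|---|---|
| 0 | 0.530 | division by zero | 0.530 |
| 0.5 | 0.406 | 0.693 | 0.406 |
| 1 | 0.293 | 0.530 | 0.293 |
| 2 | 0.132 | 0.361 | 0.132 |

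With delta = exp(Δ) the code and the text are identical. With Δ typed in directly, the code fails at 0, improves tenecteplase outcomes between 0 and 1, does nothing at 1, and penalises too weakly above 1.

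**2. Who is penalised.** Take tenecteplase patients missing Day 90 (O = observed, M = missing, for Day 5 then Day 30).

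| Pattern | Day 5 start | Day 30 start |
|---|---|---|
| O, O | penalised at Day 90 | penalised at Day 90 |
| O, M | penalised at Day 30, carried to Day 90 | the same |
| M, O | penalty used at Day 5; Day 90 unpenalised | depends on the reading |
| M, M | penalised at Day 5, carried forward | cannot be imputed (no previous mRS) |

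In the M, O row the observed Day 30 score is the previous value for the Day 90 model, so nothing imputed at Day 5 reaches Day 90. With a Day 30 start, the literal reading still makes Day 5 the first missing visit, and Day 90 is again unpenalised. Only if first missing is read as first imputed does the penalty fall on Day 90. The SAP expects such gaps: 4.9.1.2 has a rule that intermittent missing scores may not be imputed as death.

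**3. Visit sequence and patient set.** The M, M row links the two conflicts. Apart from out-of-window assessments, patients missing all three visits are those with no post-baseline mRS. The Day 30 step list therefore fits the exclusion in 4.9.1. The Day 5 start in Appendix 3 fits the all-ITT note in 4.9.1.2. The SAP states both pairs.

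**4. Size under the plan's assumptions.** Inputs: SAP Table 1, 228 per arm, and 5% of tenecteplase missing (0.05 × 228 = 11.4 patients). The 5% is the SAP's dropout rate, used here as the share missing. The tenecteplase distribution is 95% Table 1 plus 5% Table 1 with each cumulative odds multiplied by exp(−Δ); placebo is unchanged. The test is a tie-corrected, unadjusted Wilcoxon on expected counts, not the SAP's full algorithm.

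- Δ = 0: p = 0.0008
- Δ = 1: p = 0.0023
- Δ = 2: p = 0.0055
- All missing imputed as mRS 6 (the limit): p = 0.016

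The final threshold is 0.049, so nothing tips. The code line with delta 0.25 or 0.5 gives p = 0.0002 or 0.0004, a move in the wrong direction.

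**5. Illustration on assumed inputs only.** Shift the Table 1 placebo column by an assumed common odds ratio of 1.47, which gives p = 0.02, with 5% of tenecteplase missing. The result tips at Δ of about 1.2, which is exp(1.2) = 3.3 on the code's scale. If an assumed 10%, 25% or 50% of the missing tenecteplase patients follow the M, O pattern and go unpenalised, the tipping Δ rises to about 1.3, 1.7 or 2.9. The documents support neither the odds ratio nor these shares.

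**The case against.** The strongest reply is that Appendix 3 offers sample code with placeholders, that the line works on odds, and that 4.6.4.3 gives the odds-scale term as exp(−Δ). A programmer who takes delta to be exp(Δ) gets exactly the text's formula. This stands. A reader might infer that the tipping-point analysis is coded wrongly and would favour tenecteplase. The documents do not support that. It needs log-scale values typed into an odds-scale line, and such a run would expose itself by failing at 0 and by a p-value that improves between 0 and 1. What remains is a missing definition and the risk that 3.3 is reported where 1.2 is meant.

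A reader might also infer that the start visit alone decides who is penalised. That holds only if first missing means first imputed. Read literally, the M, O patient's first missing visit is Day 5 under either start. The fault lies in the penalty wording, and the start visit only interacts with it.

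It can also be said that 4.9.1 is the parent of 4.9.1.2 and covers all mRS analyses, so it governs. That is a possible reading, but the note in 4.9.1.2 says the opposite, and Appendix 3 imputes Day 5.

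Finally, the tipping values in the illustration are fragile. With starting p-values of 0.01 and 0.04 in place of 0.02, the tip falls at Δ of 2.2 and 0.28. This stands, and those figures should not be read as estimates for this trial.

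**Conclusion.** The point holds as a minor one and is confined to the tipping-point sensitivity analysis. Three things are established from the text: delta is undefined in the code and has a different null value from Δ; the once-only penalty, read literally, leaves the M, O patient unpenalised at every Δ; and the SAP gives two visit sequences and two patient sets. The second defect can only make the result look more robust.

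Under Table 1 with 5% of tenecteplase missing, the final result does not tip on either scale (p at most 0.016), so no change of conclusion is shown under the planned effect. That rests on an unadjusted Wilcoxon approximation with expected counts. The documents give no frequency for the M, O pattern or for patients with no post-baseline mRS, so their effect cannot be sized. The LOCF primary test, alpha and sample size are unaffected, and nothing here shows that the executed program was wrong.

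**What to change.** 1. **Scale.** In Appendix 3 write `newoddsr=oddsr*exp(-delta)` and start at delta = 0. Alternatively keep the line, define delta = exp(Δ), start at 1 and report ln(delta). Cost: one line or one definition.

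2. **Penalty rule.** Apply the penalty at the first missing visit after the last observed mRS, or at the first imputed visit for patients with no post-baseline mRS. Alternatively start imputation at Day 30 and define the penalty as falling on the first imputed visit. Cost: one sentence; a last-observed-visit flag may be needed in the imputation dataset.

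3. **Visits and patients, by one choice.**
   - *Day 30 start.* Keep the exclusion in 4.9.1. Correct the time index and the all-ITT note in 4.9.1.2, and the Day 5 sentence in Appendix 3. Cost: patients with no post-baseline mRS stay outside the only check for data missing not at random.
   - *Day 5 start.* Impute all ITT patients with baseline covariates. Correct the step list in 4.9.1.2, limit the 4.9.1 exclusion to the LOCF analyses, and label the Δ = 0 run as using a different patient set from the primary analysis. Cost: the added patients are imputed from baseline data alone.

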2.3 DETERMINATION OF SAMPLE SIZE

Approximately 456 patients will be enrolled in this study. Assuming the distribution of mRS scores at Day 90 in the two treatment arms as shown in [Table 1](#) and a 5% dropout rate in the study, approximately 228 patients in each treatment group will provide at least 90% power to detect the specified difference in the distribution of the mRS scores at the 2-sided 0.049 significance level (after adjustment for one efficacy interim analysis). This corresponds to being able to detect a common odds ratio (OR) of at least 1.76 (tenecteplase vs. placebo), with a total sample size of approximately 432 evaluable patients, assuming a 5% dropout rate.

Table 1 Assumed Distribution of 90-Day mRS in Use in Sample Size Determination

mRS	0	1	2	3	4	5	6
Tenecteplase (% of patients)	17	20	16	15	13	7	12
Placebo (% of patients)	13	13	12	14	18	12	18

mRS = modified Rankin Scale

The sample size estimation is highly dependent on the distribution assumption of 90-day ordinal mRS score for both treatment arms; thus, additional power calculation were performed with 456 total patients, assuming 5% drop-out rate, for different distribution scenarios on the mRS at Day 90, derived from previous stroke studies. These resulted in >88% and >99% power to detect the specified difference in the distribution of the mRS scores. For more details, see Section 6.1 of the Protocol.

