If the proportional odds hypothesis is rejected, the stratified WMW GenOR will be computed to compare the odds of having a lower mRS in the treatment group compared to placebo. This method does not require the proportional odds model assumption and is easily interpretable, computationally simple, and allows for confidence intervals to be constructed (Churilov et al. 2014). See details in [Appendix 4](#).

An unadjusted analysis of mRS distributions by treatment group will also be performed using the Wilcoxon-Mann-Whitney test (PROC NPAR1WAY) as supportive analysis.

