One efficacy interim analysis is planned for this study, when 50% (i.e., 228) of the total patients have completed the 90-day assessment to monitor both the efficacy and safety of tenecteplase vs. placebo. At the efficacy interim analysis, a type I error rate of 0.003 will be allocated for the interim efficacy evaluation based on the Lan-DeMets theory for α -spending function that approximates the O'Brien-Fleming boundary (DeMets and Lan 1994). In case of the positive efficacy result, the iDMC may recommend to stop the trial based on the benefit-risk profile of the study drug (see Section [3.3](#)). In the event that the trial is stopped due to overwhelming efficacy results from the primary endpoint at the interim analysis, final analysis of the secondary endpoints will be performed based on the hierarchical testing procedure as described in the Section [4.6.2](#) at the 0.003 level to control the studywise type 1 error. If the study continues beyond the efficacy interim analysis, the critical value at the final primary efficacy analysis would be adjusted accordingly to maintain the protocol-specified overall type I error rate, i.e., the final efficacy analysis will be performed at the 0.049 significance level to maintain an overall family-wise type 1 error rate of 0.05.

An independent statistical entity will be responsible for conducting the interim safety and efficacy analyses and preparing the reports for iDMC review. The Sponsor will remain blinded during the course of the study.

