The Wilcoxon-Mann-Whitney generalized odds ratio (WMW GenOR) statistic provides a convenient way to compare two distributions of an ordinal outcome that does not require the proportional odds assumption. It is defined as follows:

Let Y_t be a randomly selected observation of mRS from the treatment group and let Y_p be a randomly selected observation from the placebo group. WMW GenOR is the ratio of the probability that Y_t is better than Y_p , to the probability that Y_p is better than Y_t , with an adjustment for ties:

$$\alpha = \frac{P(Y_t < Y_p) + 0.5 * P(Y_t = Y_p)}{P(Y_t > Y_p) + 0.5 * P(Y_t = Y_p)}$$

An earlier work by Agresti (1980) considered a similar statistic, but did not account for the ties. This measure was discussed in Churilov et al (2014), and was shown to have superior properties in the presence of ties than Agresti's statistic. Churilov et al (2014) argued that the asymptotic properties developed by Agresti extend to the WMW GenOR statistic, but did not present the formulas for the standard error. O'Brien and Castelloe offered a way to eliminate the ties and apply Agresti's formulas directly. Details of the derivation are presented below.

1. Eliminate the ties by splitting the counts observed for mRS=k in the placebo (*i.e.* N_{2k} , $k = 0, 1, 2, \dots, 6$) group equally between $k-0.1$ and $k+0.1$ (*i.e.* $N_{2k}/2$, $k = 0, 1, 2, \dots, 6$). Thus, observed mRS will be represented by the following table, where N_{1k} , $k = 0, 1, 2, \dots, 6$, stands for the counts observed for mRS=k in the treatment group:

mRS	Treatment	Placebo
-0.1	0	$N_{20} / 2$
0	N_{10}	0
0.1	0	$N_{20} / 2$
0.9	0	$N_{21} / 2$
1	N_{11}	0
1.1	0	$N_{21} / 2$
1.9	0	$N_{22} / 2$
2	N_{12}	0
2.1	0	$N_{22} / 2$
2.9	0	$N_{23} / 2$
3	N_{13}	0

3.1	0	$N_{23} / 2$
3.9	0	$N_{24} / 2$
4	N_{14}	0
4.1	0	$N_{24} / 2$
4.9	0	$N_{25} / 2$
5	N_{15}	0
5.1	0	$N_{25} / 2$
5.9	0	$N_{26} / 2$
6	N_{16}	0
6.1	0	$N_{26} / 2$

2. Let $P_{1i} = N_{1i} / \sum_i N_{1i}$ and $P_{2i} = N_{2i} / \sum_i N_{2i}$ be the sample proportions of patients with observed mRS=i in the treatment and placebo groups, respectively, where the index i is for the mRS value from the above table, from -0.1 to 6.1. Then the WMW GenOR statistic and its variance can be computed using Agresti's (Agresti A 1980) formulas (4.1) and (4.3), respectively

$$\hat{\alpha} = \sum_{j>i} P_{1i} P_{2j} / \sum_{j<i} P_{1i} P_{2j}$$

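### The variance formula for the fallback primary test (SAP Appendix 4) overstates the placebo term, so its standard error is about 1.7% too large and the test is slightly conservative

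*SAP*

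**What the plan says.** SAP section 4.6.1 tests the proportional odds assumption first. "If the proportional odds hypothesis is rejected, the stratified WMW GenOR will be computed"; the same method applies if the proportional odds model cannot be fitted. The fallback is then the primary test, judged at 0.049 two-sided at the final analysis or 0.003 at the interim.

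Appendix 4 sets out the calculation:

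- Step 1: "Eliminate the ties by splitting the counts observed for mRS=k in the placebo" group equally between k−0.1 and k+0.1. Tenecteplase counts stay at k.
- Step 2: compute the generalized odds ratio and its variance from Agresti's formulas, with the proportions of the 21-row split table.
- Step 3: pool the log estimates over strata by inverse variance, using those same variances.

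Appendix 3 says the method will be programmed from the Appendix 4 formulas. The subgroup analyses in sections 4.6.3.1 and 4.6.5 reuse the primary methodology without re-testing proportionality, so a switch would carry into them.

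**The concern.** Splitting the counts is a neat way to get the tie-adjusted estimate from a formula that has no ties. It is not neutral for the variance. Each placebo patient has one mRS value and therefore one score against the tenecteplase arm. After the split, that patient enters the placebo variance term with two different scores, each at half weight. The spread between the two is an artefact of the table, yet it is counted as variation between patients.

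At stake are the p-value and confidence interval of what could be the primary analysis. The standard error would be too large, the test would run below its nominal level, and a result close to the threshold could be missed.

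**Working it through.** **Inputs.** mRS 0–6 percentages from SAP Table 1: tenecteplase 17/20/16/15/13/7/12, placebo 13/13/12/14/18/12/18. Sample size from SAP 2.3: "approximately 228 patients in each treatment group", "with a total sample size of approximately 432 evaluable patients, assuming a 5% dropout rate", so 216 per arm. Two-sided level 0.049, z = 1.9686.

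**Step 1. The plan's own power.** SAP 2.3 says the sample "will provide at least 90% power to detect the specified difference"; the Protocol synopsis names the Wilcoxon-Mann-Whitney test as the basis.

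- θ = P(tenecteplase lower) + ½P(tie) = 0.58955.
- Tie-corrected null SE = √[0.97838 × 433/(12 × 216²)] = 0.02751, where 0.97838 = 1 − Σp³ for the pooled distribution.
- 0.08955/0.02751 − 1.9686 = 1.287, so power is 90.1%. The stated figure is reproduced.

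**Step 2. The placebo term.** Write α for the generalized odds ratio, and P1k, P2k for the tenecteplase and placebo proportions at k. Appendix 4 gives a placebo patient at k two scores:

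- row k−0.1: s₋ = α·P1(≥k) − P1(<k)
- row k+0.1: s₊ = α·P1(>k) − P1(≤k)

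Their mean is the mid-rank score, α(P1(>k)+P1k/2) − (P1(<k)+P1k/2). Their difference is (1+α)P1k. The mean of two squares exceeds the square of the mean by (half the difference)², so the placebo term is too large by exactly

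Σₖ P2k·[(1+α)/2·P1k]²,

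which is positive whenever the arms share a category. The tenecteplase term is unaffected, because its scores already see the placebo halves as mid-ranks.

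**Step 3. One category as a check.** α = 0.58955/0.41045 = 1.4364. At k = 1, s₋ = 1.4364×0.83 − 0.17 = 1.0222 and s₊ = 1.4364×0.63 − 0.37 = 0.5349. The mean of squares is 0.6655 and the square of the mean is 0.6061. The difference, 0.0594, equals (1.2182×0.20)².

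**Step 4. All categories.** The weighted excess for k = 0 to 6 is 0.00558 + 0.00772 + 0.00456 + 0.00467 + 0.00451 + 0.00087 + 0.00385 = 0.0318 (0.03176 before rounding).

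| | Appendix 4 | One mid-rank score |
|---|---|---|
| Tenecteplase term | 0.4439 | 0.4439 |
| Placebo term | 0.5246 | 0.4928 |
| Sum | 0.9685 | 0.9368 |
| SE(log GenOR) = √[sum/(216×0.41045²)]/1.4364 | 0.1136 | 0.1117 |

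The placebo term is inflated by 6.4%, the total variance by 3.4% and the SE by 1.7%. In 400,000 simulated trials the true SD of log GenOR was 0.1120; the mean SE was 0.1139 by Appendix 4 and 0.1120 by mid-ranks. The 95% interval around 1.436 is 1.150–1.794 as written and 1.154–1.788 corrected.

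**Step 5. Level and power, unstratified.** Under the pooled null the excess is 0.0216 on a sum of 0.6523, an SE ratio of 1.0164. Actual level = 2[1 − Φ(1.9686×1.0164)] = 4.5%. Simulation gives about 4.5% as written and 4.8–5.0% corrected. At the interim level of 0.003 the actual level is about 0.0025.

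Power by formula:
- corrected: Φ(0.3621/0.1117 − 1.9686) = 89.9%
- as written: Φ[(0.3621 − 1.9686×0.1136)/0.1117] = 89.3%

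Simulation gives about 90.4% and 89.8%. The loss is 0.6 points either way.

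**Step 6. Stratified.** The SAP does not give stratum sizes or prognosis by stratum. I assumed equal strata and a baseline shift running from −1 to +1 in log-odds across them, with 432 patients:

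| Strata | Type I error, as written | Type I error, mid-rank | Power lost |
|---|---|---|---|
| 4 | 4.0% | 4.6% | 1.3 points |
| 8 | 3.8% | 4.4% | 1.3 points |
| 16 | 3.2% | 3.9% | 1.7 points |

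With no shift between strata, the same settings give 3.5–4.3% as written and 3.9–4.7% corrected.

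**The case against.** The strongest reply is that this hardly matters. The discrepancy is 1.7% of a standard error, it errs on the safe side, and it arises only if the switch occurs. Table 1 is not proportional (cumulative odds ratios run from 1.37 to 1.96), yet a rough treatment-only approximation puts the chance of rejecting proportional odds at about 17%. On that figure the unconditional power cost is near 0.17 × 0.6 ≈ 0.1 point. The SAP's score test also covers the adjusting variables, so the real chance may differ. The SAP attributes the tie-splitting to a cited source. It also plans a supportive unadjusted Wilcoxon-Mann-Whitney test that does not use the split table. All of this stands as a limit on importance. None of it corrects the formula: the algebra in Step 2 does not depend on the source, and the supportive test does not replace the primary one.

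Some stronger readings are tempting, and the documents do not support them:

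- A reader might infer that the halves are counted as separate patients. They are not. The half-counts add back to the true placebo total, so the sample size is not doubled; doubling would shrink the variance.
- A reader might infer that only tied patients are split. Every placebo count is split; the excess arises where tenecteplase patients share the category.
- A reader might infer that the fix restores the 0.049 level in the stratified analysis. It does so only in part. With 16 equal strata the corrected test still runs at 3.9%, and that remaining shortfall comes from small strata.
- A reader might infer a threat to type I error. The split can only enlarge the variance. In an extreme case of 32 assumed strata with 6–7 patients per arm, rejection at the 0.003 level was 0.0045 as written and 0.0051 corrected. That comes from unstable stratum variances, not from the split.

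**Conclusion.** The point holds as a minor one. Appendix 4 states a wrong variance for a test that "the stratified WMW GenOR will be computed to compare the odds of having a lower mRS in the treatment group compared to placebo" and that would then be the primary analysis; nothing elsewhere in the SAP corrects it. Under Table 1 with 216 per arm and no strata, the effect is equivalent to losing about 14 of 432 patients (432 × [1 − 1/1.0339]).

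The direction and the algebraic excess need no assumption beyond the arms sharing at least one mRS category. The unstratified sizes rest on Table 1. The stratified sizes, roughly 1–2 points of power, rest on my assumed strata and prognostic spread and should be read as illustrations. The estimate, the sample size and the proportional odds analysis are untouched.

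**What to change.** Keep the estimate and the stratified pooling. In the placebo term of the Appendix 4 variance, use one score per category, α(P1(>k)+P1k/2) − (P1(<k)+P1k/2), squared and weighted by P2k over k = 0 to 6.

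Equivalently, compute Var(θ) as the variance of the tie-adjusted placements of tenecteplase patients divided by n1, plus that of placebo patients divided by n2, and set SE(log GenOR) = SE(θ)/[θ(1−θ)]. Under Table 1 this also gives 0.1117.

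The cost is a few lines of SAP text and code. It should be written down before unblinding, because a correction that lowers the p-value would look data-driven if made afterwards.
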